## **RESEARCH PROTOCOL SUMMARY**

TITLE:	PEDAL; Plantar Exercise, Daily, for Lymphoedema, a single- centre, controlled, prospective, randomized feasibility trial			
Short title:	PEDAL trial			
IRAS number	265968			
Device description Study design	StepIt plantar flexion rocker pedal device. CE-marked and licensed medical device. To be used in this study for indicated purpose, namely plantar flexion exercise.Multi centre, controlled, prospective randomized feasibility			
	trial			
Primary objective	To assess the feasibility of conducting a full RCT in the future			
	
 
Participants' compliance to StepIt exercise regime and total number of steps achieved
 
Recruitment and attrition rates, willingness of patients to be randomised, response rates to questionnaires, and degrees of missing data
 
Testing of eligibility criteria and ability/willingness of clinical staff to partake in recruitment of participants
 
Adequacy of duration of follow-up (e.g. in relation to lymphoedema status)
 
			
Secondary objectives	To determine the acceptability and efficacy of the step-it pedal as an adjuvant therapy for leg lymphoedema at 6 and 12 weeks post-baseline			
	
 
Efficacy of StepIt pedal adjunct therapy vs standard care. Status leg volume difference.
 
Ankle circumference
 
Ankle range of motion
 
Lymphoedema-related quality of life
 
General quality of life
 
Patient feedback on use of the device (StepIt users only)
 
			
Patient population	A total of 24 participants, over the age of eighteen, with leg lymphoedema managed by the community lymphoedema team. Participants must have the capacity to provide informed written consent and complete patient reported outcome measures. Participants are recruited from the local Hospice at Home lymphoedema service caseload.			

	
 
12 Patient will receive treatment as usual (TaU)
 
12 Patients will receive TaU plus StepIt exercise programme intervention
 
			
	Randomisation will not be stratified.			
Sponsor	North Cumbria Integrated Care NHS Foundation Trust			
Manufacturer & funder	StepIt System AB, [name] Contact: [name], PhD, [contact]			
	[contact]			
Chief Investigator	[name], GPwSI Research, North Cumbria Integrated Care NHS Foundation Trust, R&D Department, [name] [contact]			
Co-investigators				

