#### 6. SUBJECTS

#### 6.1 Anticipated number of research subjects

This concerns a feasibility trial, and therefore the results from this study should inform a potential effect size for StepIt pedal exercise therapy, and also the degree in variance in lymphoedema volume changes (primary clinical outcome). To date, there is not sufficient published data to gain an insight in the effect that calf muscle exercise may have on lymphoedema symptoms. Guidance from a publication by Julious (2005) advises the use of 12 participants per treatment arm, and this approach will be taken here (see Table 5). Patient withdrawal rates before week 12 are not known at present and measuring this will be a primary aim

Table 5, sample size numbers required, based on hypothetical differences between published data and study outcomes

	Standard (control) arm	care	Standard care plus Steplt pedal arm
Patients (n)	12		12

Since this concerns a randomised controlled trial, albeit in the shape of a feasibility study, reprting will be done in line with CONSORT guidelines (Schulz, Altman & Moher 2010). The number of patients screened but who did not meet the inclusion criteria or who declined to participate will be recorded, as will any patients who are lost to follow-up (Appendix 2).

The patient attrition rate (withdrawal and loss to follow-up) will also be recorded, since this involves a study with at multiple visits, albeit incorporated into standard clinical appointments. Patients will be recruited from the adult (age 18+) population routinely seen by the evaluating clinical staff members.

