#### 6.1.1 Randomisation

A 1:1 allocation to the control and intervention group respectively will be applied. Following written consent patients will be allocated at random to the control or intervention group, using a non-restricted randomised sequence generated for the whole sample using a free ware randomisation programme, see https://www.randomizer.org/. Sequential envelopes with each next randomisation allocation will be used to achieve concealment.

The researcher/lymphoedema care specialist will inform the patient what arm they have been allocated. As the study involves the Clinical Lymphoedema Specialist or Researcher consenting and following up patients and a self-administered intervention of necessity it is not possible to achieve blinding for the participants or the Clinical Lymphoedema Specialists.

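### The non-restricted randomisation sequence in Section 6.1.1 does not secure the 12 and 12 participants fixed in the summary and Section 6.1

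*Protocol*

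**What the plan says.** The Research Protocol Summary gives the total, "A total of 24 participants, over the age of eighteen, with leg lymphoedema", and divides it into fixed numbers: "12 Patient will receive treatment as usual (TaU") and "12 Patients will receive TaU plus StepIt exercise programme intervention". Section 6.1 gives the only basis for the size. It says that published guidance on pilot studies "advises the use of 12 participants per treatment arm, and this approach will be taken here", and Table 5 lists 12 and 12 as the numbers required. There is no power calculation, and the same section says that "Patient withdrawal rates before week 12 are not known at present".

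Section 6.1.1 sets the method: "A 1:1 allocation to the control and intervention group respectively will be applied", "using a non-restricted randomised sequence generated for the whole sample using a free ware randomisation programme", with sequential envelopes for concealment. The summary adds: "Randomisation will not be stratified". The protocol mentions no blocks, no list fixed at 12 and 12, no over-recruitment and no rule for unequal arms.

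**The concern.** An unrestricted sequence is normally one in which each patient is allocated independently, here with probability one half. The ratio is then 1:1 in expectation, and the arm sizes are left to chance. The protocol nevertheless states the arm sizes as fixed numbers and rests its sample size on them.

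Two of the trial's purposes depend on how many patients each arm holds. Compliance with the exercise regime is the first primary outcome in Section 5.5.1, and the summary couples it with the total number of steps. Only StepIt patients can supply either, and Section 8.3 divides that arm further by adherence. Section 6.1 also wants the trial to inform the variability of leg volume change, and an estimate made within one arm depends on that arm's size. The 24 contain no allowance for dropout, so a chance shortfall would come on top of withdrawals.

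**Working it through.** **Inputs.** Total n = 24, planned arms 12 and 12 (summary; Section 6.1, Table 5). Allocation 1:1, sequence unrestricted (Section 6.1.1). No stratification (summary).

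**The plan's own figure.** 12 per arm × 2 arms = 24, which agrees between the summary and Section 6.1. No significance level, power, effect size or standard deviation is given, so there is nothing further to reproduce.

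**Reading A: simple randomisation.** Let X be the size of the StepIt arm, X ~ Binomial(24, 0.5).

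- P(12/12) = C(24,12)/2^24 = 2,704,156/16,777,216 = 16.1%.
- P(one arm below 12) = 100% − 16.1% = 83.9%.
- P(StepIt arm below 12) = 83.9%/2 = 41.9%, by symmetry. The StepIt arm is equally likely to exceed 12.
- P(smaller arm ≤ m) = 2 × Σ C(24,k)/2^24 for k = 0 to m. For the StepIt arm specifically, halve it.

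| Smaller arm | Either arm | StepIt arm |
|---|---|---|
| 10 or fewer | 54.1% | 27.1% |
| 9 or fewer | 30.7% | 15.4% |
| 8 or fewer | 15.2% | 7.6% |
| 7 or fewer | 6.4% | 3.2% |

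The expected size of the smaller arm is 10.1. If simple randomisation were kept, both arms would reach 12 with probability 92.0% at a total of 33 and 95.9% at a total of 35.

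**Reading B: one random ordering of 12 + 12 assignments.** The arms close at exactly 12 and 12 once all 24 are randomised, so the shortfall is 0%. Such a list is restricted.

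**Effect on the arm difference.** The standard error relative to 12/12 is √[(1/a + 1/b)/(1/12 + 1/12)]:

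- 10/14: 1.014 (+1.4%)
- 9/15: √(0.1778/0.1667) = 1.033 (+3.3%)
- 8/16: √(0.1875/0.1667) = 1.061 (+6.1%)

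**Effect within one arm.**

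- The upper limit of the 95% interval for a standard deviation is the estimate times √(df/χ²), with χ² the 2.5% quantile on df = n − 1. With 12 patients the factor is √(11/3.816) = 1.70. With 8 it is √(7/1.690) = 2.04.
- For a compliance proportion, assumed to be 50% because the protocol gives none, the approximate 95% half-width is 1.96 × √(0.25/n). That is 28 percentage points with 12 patients and 35 with 8.
- A standard deviation pooled over both arms has 24 − 2 = 22 degrees of freedom at 12/12 and at 8/16 alike, so the split does not affect it.

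**The case against.** The strongest defence is that Section 6.1.1 can be read another way. A sequence generated for the whole sample, beside a 1:1 ratio and stated arms of 12, could be a single shuffled list of 12 + 12 without blocks or strata. The shortfall would then be zero. This stands as a possible reading, and the 84% is therefore conditional. It does not rescue the text, because a list constrained to 12 and 12 is not unrestricted.

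It can also be said that simple randomisation is valid and unbiased, and that it is the least predictable method in an open-label trial. Twelve per arm is a rule of thumb with no power attached. Most primary outcomes (recruitment, attrition, willingness to be randomised, questionnaire response, missing data) are measured across the whole trial and hardly depend on the split. Section 6.1 does not ask for a separate variance in each arm. All of this stands and limits the harm.

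A reader might infer more than the protocol supports:

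- **That 12 and 12 is impossible.** It is not: simple randomisation reaches it about one time in six.
- **That the StepIt arm has an 84% chance of being short.** That figure counts either arm; for StepIt it is 42%.
- **That device acceptability is a primary outcome put at risk.** The summary and Section 4.2 make acceptability a secondary objective.

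**Conclusion.** The point holds as an inconsistency between the stated size and the stated method. On the literal reading, which is also the usual one, the method probably misses 12 and 12: 84% for either arm, 42% for StepIt. On the other reading the arm sizes are safe and the description of the sequence is wrong. The protocol does not settle which was meant, so the wording needs correcting either way.

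The consequence is modest. The comparison between arms stays valid and loses about 3% in standard error at 9/15 and 6% at 8/16. The real cost is in estimates made within the smaller arm, above all compliance and step counts if that arm is StepIt.

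The probabilities assume independent allocation at one half and exactly 24 patients randomised. They take no account of dropout, which the protocol says is unknown and which could only reduce the numbers further.

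**What to change.** **If the list is not yet in use**, replace the description in Section 6.1.1 with a concealed, restricted 1:1 list that totals 12:12. Either of two forms will do:

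- one random permutation of 12 + 12 assignments;
- randomly permuted blocks of mixed size, not disclosed to recruiting staff and chosen to sum to 24, for example three blocks of 4 and two of 6 (12 + 12 = 24) in random order. Blocks of 4 and 6 drawn freely need not end at 24 and would not guarantee the balance.

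The cost is one sentence and a new list. The drawback is slightly more predictability near the end of a block, or of the list, since staff in an open-label trial know the earlier allocations. Undisclosed mixed sizes limit this.

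**If the list is already in use**, do not force the remaining allocations to close at 12 and 12. This version is dated November 2021 and Table 2 plans recruitment from December 2019 or January 2020, so use may well have begun. Forcing could make late allocations predictable: at 12/6, the last six would all go to one arm. It is impossible once an arm exceeds 12. Instead, state how the list was generated, and reword the summary, Section 6.1 and Table 5 so that 12 per arm is the expected size, not the fixed one. This costs only wording.

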#### 6.2 Eligibility criteria

#### 6.2.1 Inclusion criteria

- Over the age of 18
- Diagnosis of chronic leg lymphoedema (chronicity > 3 months). This includes primary or secondary lymphoedema.
- Lymphoedema can be present in one leg or both legs
- Newly presenting leg lymphoedema patients or existing patients.
- Same type of compression therapy for at least 2 months.
- Presence of leg ulcer is not an exclusion criterion
- Command of English , verbal and in writing
- Able to give informed consent

#### 6.2.2 Exclusion criteria

- Under the age of 18 years
- Unable to fully understand the consent process and provide informed consent due to either language barriers or mental capacity
- Currently receiving, or within 6 months of receiving, chemotherapy or radiotherapy for cancer
- Surgery on lower limb within last three months
- Surgery within last month.
- BMI > 50 (ie extreme obesity; approximation using 'Malnutrition Universal Screening Tool' ('MUST') is allowed)
- Active infection in one or both of the legs treated with systematic antibiotics (or within one week of finishing antibiotics)
- Inability to comply with the StepIt pedal exercise, eg due to fixed ankle or other pathology that impedes using the StepIt pedal. This will be established during the screening/consent process by trialling the StepIt pedal and the movement involved in clinic.
- Commenced, or change in dosage of, diuretic medication in last

#### 6.3 Early withdrawal of subjects + intervention suspension

Patients have the right to withdraw from the trial at any time and without giving any reason. If a patient withdraws from the trial, any and all information gathered prior to the withdrawal will be included in the analysis, but no further data collection will occur. If a patient does not attend a planned follow-up appointment then two more attempts will be made to contact the patient regarding the study. If still no contact can be made then the patient is deemed lost to follow-up and any collected study data will be retained.

If a patient needs to suspend the StepIt exercises then this does not change the planned follow-up dates for 6 and 12 weeks after baseline study visit. This may be eg hospital admission. If a patient develops an infection then the routine approach will be: rest of the legs (ie no StepIt exercises) for duration of antibiotics course + 1 week. Intervention suspension events will be recorded.

#### 7. SAFETY

#### 7.1 Potential risks & benefits to study participants

There is no anticipated personal safety risk associated with taking part in this study. If the research team learns of important new information that might affect patient's desire to remain in the study, he or she will be told. Appropriate precautions are in place to ensure medical and personal information is kept safe through adhering to appropriate governance regulations. Participants in the StepIt intervention group will be asked to do the StepIt exercise; this will take more time and effort compared to standard management (treatment as usual). Any adverse events will be recorded, as outlined in sections below.

For the participants in the control group there is no direct benefit in taking part in this study. They will be cared for in exactly the same manner as they normally would. For participants in the Step It intervention group, there may be benefits in terms of improved lymphoedema symptoms compared to normal standard care. However, this has not yet been proven and established, and this study is aimed to assess this. Participants cannot claim payments, reimbursement of expenses or any other benefits or incentives for taking part in this research.

#### 7.2 Safety definitions

Adverse Event (AE)	Any untoward medical occurrence in a patient or other clinical investigation participant taking part in a trial of a medical device, which
	does not necessarily have to have a causal relationship with the device under investigation.
	An AE can therefore be any unfavourable and unintended sign
	(including an abnormal laboratory finding), symptom or disease
	temporally associated with the use of the device, whether or not
	considered related to the device.
Serious Adverse Event	A serious adverse event is any untoward medical occurrence that:

 results in death
 is life-threatening
 requires inpatient hospitalisation or prolongation of existing hospitalisation
 results in persistent or significant disability/incapacity
 consists of a congenital anomaly or birth defect.
 Other 'important medical events' may also be considered serious if they jeopardise the participant or require an intervention to prevent one of the above consequences.
 NOTE: The term "life-threatening" in the definition of "serious" refers to an event in which the participant was at risk of death at the time of the event; it does not refer to an event which hypothetically might have caused death if it were more severe.

#### 7.3 **Procedures for recording adverse events**

All AEs need to be reported to the sponsor/host Trust R&D within one week of the investigator team becoming aware of them. For this purpose an AE report form is completed by the researcher and/or Chief Investigator. SAEs should be reported within one working day of becoming aware of the event, where possible.

The relationship of each adverse event to the trial must be determined by the Chief Investigator, a medically qualified individual, according to the following definitions:

- **Related**: The adverse event follows a reasonable temporal sequence from swabbing. It cannot reasonably be attributed to any other cause.
- **Not Related**: The adverse event is probably produced by the participant's clinical state or by other modes of therapy administered to the participant.
- Severity grading: the Chief Investigator will also record if it concerns an AE or SAE.

This is recorded on the aforementioned AE reporting form. The forms are stored in the study site file.

Pseudo-anonymised copies of all adverse events forms will be shared with StepIt AB as soon as causality reporting has been performed and concluded.

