#### 5.3 Recruitment

Participants will be randomised to either the control group (standard care) or the intervention group (standard care plus use of a StepIt pedal) for 12 weeks. Patients in both groups will be given the usual lymphoedema management information, but those in the intervention group will be issued with a StepIt Pedal to use daily for foot and ankle exercises. The participants will be asked to report on their activity at the end of trial (self-reported compliance Likert scale question). At their discharge visits participants are also asked to provide their wider opinion on trial participation. All participants will have demographic data obtained and the following base line measures (Table 3):

T	able	3.	Baseline	measures
•	abic	٠.	Duschine	measures

Weeks	0	6#	12#
Leg volume	Х	Х	Х
Ankle circumference	Х	Х	Х
Ankle range of motion	Х		Х
Visual analogue pain score	Х	Х	Х
LYMQOL-Leg	Х	Х	Х
EQ-5D-5L	Х	Х	Х
PEDAL experience questionnaire			Х

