#### Trial-related outcome measures

- Participants' compliance to StepIt exercise regime
- Recruitment and attrition rates, willingness of patients to be randomised, response rates to questionnaires, and degrees of missing data
- Testing of eligibility criteria and ability/willingness of clinical staff to partake in recruitment of participants

- Ability of site and clinicians to recruit and randomise patients, irrespective of care setting
- To assess any training requirements
- Adequacy of duration of follow-up (e.g. in relation to lymphoedema management and outcomes)
- Fitness for purpose of data collection methods including across and between care settings
- Adverse events

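### Section 7.3 ties a related adverse event to swabbing, which this trial does not do, and its two causality categories do not cover every event

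*Protocol*

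**What the plan says.** Protocol section 7.3 makes the causality call compulsory and says how it is made: "The relationship of each adverse event to the trial must be determined by the Chief Investigator, a medically qualified individual, according to the following definitions".

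Two causality definitions follow.

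- The category Related is given as: "The adverse event follows a reasonable temporal sequence from swabbing. It cannot reasonably be attributed to any other cause". This sets two conditions, one on timing and one on the absence of any competing explanation.
- The category Not Related sets a single condition, worded as follows: "The adverse event is probably produced by the participant's clinical state or by other modes of therapy administered to the participant".

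There is no third causality category. The remaining item in that list only records whether the event is an AE or an SAE.

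Section 7.2, directly before it, takes a different reference point. Its adverse event definition covers any unfavourable sign, symptom or disease "temporally associated with the use of the device, whether or not" it is judged to be related to the device.

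On the intervention, section 5.3 states that "those in the intervention group will be issued with a StepIt Pedal to use daily for foot and ankle exercises". Section 5.5.1 lists "Adverse events" among the primary, trial-related outcome measures. On onward reporting, section 7.3 adds: "Pseudo-anonymised copies of all adverse events forms will be shared with StepIt AB as soon as causality reporting has been performed and concluded".

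**The concern.** The definition of Related needs a reference exposure, so that the assessor can ask whether the event followed it in a plausible time. Section 7.3 names an exposure that no participant receives. It looks like text carried over from another protocol, although that is an inference.

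The second problem is independent of that word. Related demands that no other cause be reasonable; Not Related demands that another cause be probable. These are not complements, and nothing covers the ground between them. The protocol allows participants with leg ulcers (6.2.1) and expects comorbidities such as heart failure, diabetes and venous or arterial disease (8.1). Competing explanations for an event in the leg are therefore plausible, though the documents do not say how often they would be possible without being probable.

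At stake is whether the relatedness call on the adverse event form means anything, in a study that describes itself as the first use of this pedal in leg lymphoedema (section 2). The Chief Investigator makes the call, and the protocol describes no second causality assessment. Section 9 states that no steering committee will be convened.

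**Working it through.** No arithmetic applies, and the plan has no figure to reproduce. The check is one of text and logic.

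**Step 1: is there any swabbing in the trial?** The places where it would appear are:

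- Section 3 (device and intervention): pedal exercise with a clipped-on pedometer.
- Section 5.2 (screening and consent): a trial of the pedal movement.
- Section 5.3, Table 3 (schedule): leg volume, ankle circumference, ankle range of motion, pain score, LYMQOL-Leg, EQ-5D-5L and an experience questionnaire.
- Section 5.5 (outcomes), section 8 (analysis) and Appendix 1 (tools): no swab.

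The word occurs only in section 7.3.

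**Step 2: write the definitions as conditions.**

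- T: the event follows the named exposure in a reasonable time.
- N: no other cause is reasonable.
- P: the participant's clinical state or another therapy is the probable cause.

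Related = T and N. Not Related = P.

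**Step 3: apply them to events that occur in a plausible time after pedal use.**

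| Other cause | As written (exposure = swabbing) | Word corrected (exposure = pedal) |
|---|---|---|
| None reasonable | T fails, P fails: no category | T and N hold: Related |
| Possible, not probable | T and N fail, P fails: no category | N fails, P fails: no category |
| Probable | P holds: Not Related | P holds: Not Related |

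As written, T fails in every row, so Related is empty and two of the three rows have no category. With the word corrected, one row of three still has none. These are rows of a logical table, not expected proportions of events.

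**Step 4: what depends on the label?**

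- Recording and reporting to the sponsor (7.1, 7.3): every adverse event, whatever its causality.
- Sharing with the manufacturer (7.3): all forms. The causality call settles when a form is sent, not which forms are sent.
- Analysis (8.2, 8.3): no use of the related/not-related split.
- Outcome list (5.5.1): adverse events as such, not related ones only.

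**The case against.** The strongest defence is that a sensible reader will see a slip. Section 7.3 asks about relationship to the trial, the assessor is medically qualified, and section 7.2 speaks of device use. In a trial with a pedal and no swab, the assessor would probably substitute the pedal. That is fair as a forecast of practice, and it means that the empty Related category is a consequence of the literal text, not a predicted result. It does not rescue the text. The definitions are mandatory, section 10.1 rules out deviating without prior approval except for an immediate hazard, and a silent substitution leaves the rule actually applied undocumented. Nor does it touch the gap between the two categories.

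The defence is stronger on consequences, and there it largely stands. A reader might infer that device-related harm will be recorded as zero, or that the full RCT will inherit a false safety conclusion. The documents support neither. An event caused by the pedal would fail both definitions, so a recorded zero is not the necessary outcome. Leg infection, pain, leg volume and ankle circumference are outcomes in their own right (5.5.2), intervention suspensions are recorded (6.3), and the randomised control arm allows harms to be compared whatever label they carry. A reader might also infer that the causality call decides what the manufacturer sees; section 7.3 sends all forms.

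A confidence limit for zero related events among 12 pedal users would not size the problem either. It describes the number of users and would be the same in any trial with that many.

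**Conclusion.** The point holds as a defect in an operative safety definition. Section 7.3 conflicts with section 7.2 and with the intervention itself. Read literally it leaves an event caused by the pedal without a valid category, and even with the word corrected it leaves out events with a possible but not probable other cause. What is compromised is the validity of the causality classification, not the capture of events. Sample size and efficacy analyses are unaffected. It should be fixed, but it does not invalidate the trial.

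This rests on two conditions. First, the parts that cannot be seen (removed front matter and the flowcharts in Appendices 2 and 3) contain no swabbing procedure; nothing in the visible schedule, intervention or outcome sections suggests one. Second, the adverse event form, which is not reproduced, does not already carry a different, complete definition.

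**What to change.** 1. In section 7.3, replace the reference to swabbing with use of the StepIt pedal or a study procedure, in line with section 7.2.
2. Make the two categories jointly exhaustive, for example by defining one as every event that does not meet the other. Where the threshold lies is for the sponsor to choose. The strict standard now used for Related is not contradicted elsewhere in the protocol, so a looser one is an option and not part of the correction.
3. Align the adverse event form with the new text.
4. Re-review any event already classified. This version is dated November 2021 and Table 2 anticipates recruitment from December 2019 or January 2020, so there may be some.

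The cost is a small amendment to the text and form and a brief re-review. Depending on the threshold chosen, more events may be classed as related.

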#### 5.5 **Outcome measures**

#### 5.5.1 **Primary outcome measures**

To assess the feasibility of conducting a full RCT in the future, the primary outcome measures are mainly:

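### Section 7.3 records seriousness under the label of severity, and the protocol defines no intensity grade for adverse events

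*Protocol*

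**What the plan says.** Section 7.3 (Procedures for recording adverse events) lists what is determined for each event. After two categories of relatedness comes the item on severity: "Severity grading: the Chief Investigator will also record if it concerns an AE or SAE". The section adds: "This is recorded on the aforementioned AE reporting form". The form itself is not part of the protocol.

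Section 7.2 (Safety definitions) sets out what makes an event an SAE. The criteria are consequences: death, threat to life, lasting disability, congenital anomaly, other important medical events, and an event that "requires inpatient hospitalisation or prolongation of existing hospitalisation". The note beneath explains that the term life-threatening concerns actual risk of death at the time, and that "it does not refer to an event which hypothetically might have caused death if it were more severe".

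Section 5.5.1 opens with "To assess the feasibility of conducting a full RCT in the future, the primary outcome measures are mainly" and closes its list of eight trial-related measures with "Adverse events".

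**The concern.** Severity (how intense an event is) and seriousness (what it leads to) are different properties, and section 7.3 fills the first with the second. Severe calf or ankle pain managed at home would usually meet no SAE criterion and is entered at the lower level. A short admission for a mild, unrelated problem is entered at the higher level.

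What is at stake is the description of tolerability. The protocol itself anticipates discomfort from the pedal: under section 5.2, significant discomfort when trying it at screening excludes a patient. Discomfort that arises later would mostly be non-serious. In a trial meant to inform a decision on a full RCT, it would be useful to know whether such events were trivial or severe, and the stated rule does not record that. Under section 7.3, copies of the forms also go to the manufacturer, so a mislabelled grade would travel with them.

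**Working it through.** No figure in the plan bears on this point. The sample size rests on a rule of thumb that "advises the use of 12 participants per treatment arm" and does not depend on how adverse events are graded. The check is a comparison of definitions.

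**Step 1. What the severity item can contain.** Section 7.3 allows two values, AE or SAE.

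**Step 2. What separates the two values.** Section 7.2 separates them by consequence. Intensity is not among the criteria. The note on life-threatening events treats being more severe as something other than being serious, so section 7.3 blurs a distinction that section 7.2 draws.

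**Step 3. Cross the two properties.**

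| Intensity | Meets an SAE criterion in 7.2? | Entry under 7.3 |
|---|---|---|
| Mild | No | AE |
| Severe | No | AE |
| Mild | Yes (e.g. short admission) | SAE |
| Severe | Yes | SAE |

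Rows 1 and 2 differ in intensity and receive the same entry. Rows 2 and 3 are ranked in the wrong order if the entry is read as severity. This follows from the definition and needs no assumed number of events.

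**Step 4. Is intensity defined elsewhere?** Three other scales in the protocol concern severity, and none grades an adverse event:
- the clinician's oedema score (section 5.5.2, Table 4) grades oedema;
- the lymphoedema stage from 0 to 3 (section 8.1) is a baseline characteristic;
- the visual analogue scale (Appendix 1) asks about leg pain over the last week, at weeks 0, 6 and 12.

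**Step 5. Do other records fill the gap?** Partly.
- Section 6.3 has suspensions of the intervention recorded.
- Section 8.2 reports numbers completing and discontinuing, with reasons for the latter.
- Section 5.5.1 includes compliance with the exercise.
- Section 5.3, Table 3 includes an experience questionnaire at week 12.

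These show whether some participants paused or stopped, and how they found the pedal. None grades the intensity of an individual event, and section 6.3 does not require a suspension to be tied to an adverse event entry.

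**The case against.** The strongest reply is that this is a slip of terminology with little consequence. The AE/SAE split is the right variable for what the protocol does with it, namely reporting within one week or within one working day. Section 8 plans no analysis by severity. Adverse events are the last of eight measures, are introduced as being mainly primary, and do not appear in the summary's list under the primary objective. In a 24-patient feasibility trial of a CE-marked device, a three-level scale may look like preference.

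Much of this stands. Safety reporting is not impaired, and no test or sample size is affected. What does not fall away is that a field labelled severity holds something else, for a measure that section 5.5.1 lists as primary. A reader of the eventual report would take the label at face value.

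A reader might infer more: that the form has no place for intensity, that the information is lost for good, or that the trial could not tell trivial effects from those that stop the exercise. The documents do not support these readings. The form is not shown and may hold an intensity field or free text. Suspensions and reasons for discontinuation are recorded, so exercise-stopping effects can be partly identified. The supportable statement is that the protocol neither defines an intensity grade nor secures its collection.

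The unseen statistical analysis plan does not answer the point. It governs analysis, and cannot supply a grade that was not collected.

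**Conclusion.** The point holds as an error of definition with a limited consequence. Section 7.3 assigns a severity value that is really seriousness. By that value all non-serious pedal effects are alike, and a mild event leading to admission outranks a severe one that does not. The size is qualitative: two levels, neither of which measures intensity. The loss is in what can be said about the intensity of adverse events by arm. It does not extend to reporting deadlines, planned tests, or the ability to count events and SAEs.

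This rests on the text of the protocol alone. If the adverse event form already has a defined intensity field, what remains is the wrong label and the absence of that field from section 7.3. The correction is worth making because adverse events are a listed feasibility measure and the Chief Investigator already assesses every event.

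**What to change.** In section 7.3 and on the adverse event form, replace the single item with two:
- *Seriousness: AE or SAE, as defined in section 7.2.*
- *Severity: mild, moderate or severe*, with each level defined, and a cross-reference to any intervention suspension recorded under section 6.3.

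State that adverse events will be reported by arm, by seriousness and by severity separately. This changes recording and reporting only and touches no rule on treatment or its suspension.

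The cost is small but not nil. Section 10.1 requires review before a departure from the approved protocol, so an amendment is needed. This version is dated 24 November 2021 and Table 2 anticipates recruitment until December 2022, so on that timeline the new grade would start mid-recruitment. Events already recorded would have to be graded retrospectively from the forms, where these allow it, or reported as ungraded, and the report should say which was done. Relabelling the existing item needs no new data.
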